#### 2.5.5 Sensitivity analyses

The following sensitivity analyses will be performed for the primary estimand, to assess the robustness of the estimation in the presence of deviations from the assumptions specified in the primary analysis on the FAS only:

| Novartis | Confidential | Page 18 of 37           |
|----------|--------------|-------------------------|
| SAP      |              | Study No. CKJX839A1GB01 |

• Linear mixed-effect model for repeated measures (MMRM) analysis without multiple imputation

Analyses using the MMRM will include fixed effects for treatment, visits, interaction between treatment and visits, baseline LDL-C and interaction between baseline LDL-C and visit. Day 90 and 270 will be included as visit. The Restricted Maximum Likelihood (REML) estimation approach will be used with covariance structure set as "Unstructured". If the model does not converge with unstructured covariance matrix, the compound symmetry covariance matrix will be used in the mixed model.

As a sensitivity analysis, the imputation algorithm will be changed from a regression approach to a multivariate normal model to include in the imputation information that is provided by undetectable LDL-C values. An LDL-C value is undetectable when either

are outside of the limit of detection. Based on the limit of detection and through Friedewald's formula, a range for an LDL-C value can be calculated. In this sensitivity analysis, the LDL-C range is considered in the imputation model. As for the primary analysis, undetectable LDL-C values for either study arm are imputed under a MAR assumption, missing values in the placebo arm are imputed under a MAR assumption, and missing data on Day 270 or after treatment discontinuation in the inclisiran arm are imputed using a wash-out model (i.e., using a jump-to-reference approach).

In the sensitivity analysis, imputed baseline values will be restricted to  $\ge 0.1$  to avoid imputed values close to zero which can lead to numerical instabilities in the analysis of percentage LDL-C change from baseline.

The imputation will be carriedout using in SAS/R as mentioned in Appendix 5.5.2.

The analysis will be carried out using ANCOVA procedure as mentioned in section 2.5.2.

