6.1.3 Treatment groups

Participants will be assigned at the baseline/screening visit to one of the following three treatment groups in a ratio of 1:1:1.

- **Group 1:** Participants will continue to receive their lipid-lowering background therapy plus behavioural support (see Appendix 1)
- **Group 2:** Participants will continue to receive their lipid-lowering background therapy plus inclisiran for injection (delivered in an injection-only model)
- **Group 3:** Participants will continue to receive their lipid-lowering background therapy, plus inclisiran for injection (delivered in an injection only model), plus behavioural support (see Appendix 1)

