#### 2.5.2 Statistical hypothesis, model, and method of analysis

The primary effectiveness objective of this study is to demonstrate superiority of each inclisiran arm compared to control in terms of the percentage change from baseline in LDL-C to Day 270 in adults with elevated LDL-C. The statistical hypotheses that will be tested for each inclisiran arm are as follows:

- $H_0$ : The difference between participants treated with inclisiran and control in the least squares mean percentage change from baseline to the Day 270 visit in LDL-C= 0
- $H_a$ : The difference between participants treated with inclisiran and control in the least squares mean percentage change from baseline to the Day 270 visit in LDL-C < 0

The primary objective will be achieved if null hypothesis  $(H_0)$  rejected at the one-sided significance level of 0.025.

The primary analysis will use an analysis of covariance (ANCOVA) model on the percent change in LDL-C from baseline to Day 270 to test the superiority of inclisiran over control after missing data imputation.

Due to probable heterogeneity of variances between treatment groups, ANCOVA model which assumes unequal variances for treatment group will be used. The model will include the fixed effects of treatment group with baseline LDL-C as a covariate.

Multiple imputation will be used to impute missing data using a washout model specified in Appendix 5.5.1. A total of 500 imputed datasets will be created. The ANCOVA model will be fitted to each imputed dataset, and results will be combined using Rubin's combination rules. The estimate and corresponding 2-sided 95% confidence intervals of mean difference between treatment groups will be calculated. p-value for hypothesis test for mean difference will also be provided. The FAS will be used for this analysis. The family-wise error rate for comparisons of the two inclisiran arms with the lipid-lowering background therapy plus behavioural support arm will be controlled using the Holm procedure.

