## 3 Sample size calculation

The primary effectiveness endpoint of the study is percent change of LDL-C from baseline. However, the sample size is driven by patient experience (CSQ-8) and patient activation (PAM); two key secondary outcomes in this trial.

The trial has been powered to detect differences equivalent to a Cohen's effect size of 0.3, approximating a 'small-to-medium' effect in conventional terms

A sample size of 300 patients per arm would be able to detect this effect size with 90% power using a one-sided significance level of 0.025 (this includes a 20% allowance for drop-out in this primary care setting).

This sample size could also detect a reduction of at least 10% change of LDL-C from baseline in the inclisiran group compared to the control group (assuming a standard deviation of 30% in the control group and 20% in the inclisiran group based on observed results from previous inclisiran studies).

The total sample size for the study will be 900 participants.

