• Baseline value of efficacy measurement (continuous)

| Novartis | Confidential | Page 32 of 37           |
|----------|--------------|-------------------------|
| SAP      |              | Study No. CKJX839A1GB01 |

For each undetectable LDL-C value, a range is determined based on Friedewald's formula. Below table will provide example range calculation when

are distributed in different categories.

As a next step, the undetectable LDL-C values are baseline are imputed to create 500 complete sets of baseline LDL-C values. The imputation is performed by fitting a normal distribution to all available baseline LDL-C values including the LDL-C ranges. The imputed values are obtained by sampling from the posterior predictive distribution. As prior distribution for mean and the standard deviation a normal distribution (mean=0, sd=10) and a half-t-distribution (df=3, scale=2.5) are chosen.

To create 500 complete data sets of baseline and post-baseline LDL-C data sets, the following approach is performed for each of the 500 data sets with complete baseline LDL-C data.

- 1. Fit a Bayesian linear mixed model to all available post-baseline LDL-C data including the LDL-C ranges from Day 90 and Day 270.
  - a. The model includes study arm, visit, and baseline LDL-C as well as all interactions as fixed effects.
  - b. The model includes a normally distributed patient-specific random effect and a normally distributed residual error. The variance of the residual error differs by study arm and visit.

| Novartis | Confidential | Page 34 of 37           |
|----------|--------------|-------------------------|
| SAP      |              | Study No. CKJX839A1GB01 |

- 2. For the missing values or undetectable LDL-C values of patient *i* at visit *j* in study arm *k* that are imputed under the MAR assumption, the imputed value is drawn from the posterior predictive distribution of the outcome (i.e., LDL-C) of patient *i* at visit *j* in study arm *k*.
- 3. For the missing values of patient *i* at visit *j* in the inclisiran arm that are imputed under the jump-to-reference assumption, the imputed value is drawn from the posterior predictive distribution of the outcome (i.e., LDL-C) of patient *i* at visit *j* whereas the components (e.g., fixed effects and random effects) of the posterior predictive distribution that are associated with the inclisiran arm are replaced by the corresponding value from the placebo arm.

The above imputation will be carried out using R software.

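### The MMRM covariance is not specified by arm although the SAP expects unequal variances; fitted as one three-arm model, it would give intervals against control about 6.6% too narrow

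*SAP*

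**What the plan says.** The MMRM in SAP 2.5.5 is a sensitivity analysis for the primary estimand, run on the FAS without multiple imputation. Its mean model has "fixed effects for treatment, visits, interaction between treatment and visits, baseline LDL-C and interaction between baseline LDL-C and visit", with Day 90 and Day 270 as the visits. On the covariance the SAP says: "The Restricted Maximum Likelihood (REML) estimation approach will be used with covariance structure set as" unstructured. If that fails to converge, "the compound symmetry covariance matrix will be used in the mixed model". Neither sentence mentions grouping by treatment. SAP 2.5.6 refers back to this model for the supplementary estimand.

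Elsewhere the SAP is explicit that variances may differ by arm:

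- Primary analysis (SAP 2.5.2): "Due to probable heterogeneity of variances between treatment groups, ANCOVA model which assumes unequal variances for treatment group will be used".
- Imputation model for undetectable LDL-C (SAP Appendix 5.5): "The variance of the residual error differs by study arm and visit".
- PAM (SAP 2.6.2): the ANCOVA also assumes unequal variances by treatment group.
- Sample size (SAP 3): "assuming a standard deviation of 30% in the control group and 20% in the inclisiran group", taken from earlier inclisiran studies.

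Allocation is to "three treatment groups in a ratio of 1:1:1" (Protocol 6.1.3).

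**The concern.** An unstructured covariance with no grouping option ordinarily means one matrix estimated from all participants. Equal allocation is often taken to protect a pooled-variance comparison against unequal variances. That holds for two arms. With three arms, two of them low-variance, the pooled estimate is pulled towards the inclisiran value and understates the variance of any contrast that involves control.

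What is at stake is how the robustness check is read. The MMRM is there to replace the washout imputation with a likelihood analysis under missing at random. If it also drops the arm-specific variances, any difference in interval width from the primary has two causes that cannot be separated, and one of them makes the MMRM look too precise.

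**Working it through.** **Inputs.** SDs of 30 (control) and 20 (each inclisiran arm) percentage points, 300 per arm and 20% drop-out (SAP 3); 1:1:1 allocation (Protocol 6.1.3). The SDs are treated as residual SDs. If baseline adjustment shrinks both in proportion, the ratios below do not change.

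**The plan's own figure.** For an effect size of 0.3, 90% power and one-sided 0.025, n = 2(1.960 + 1.282)²/0.3² ≈ 234 per arm. Dividing by 0.8 gives 293, in line with the stated 300. After 20% drop-out, 300 × 0.8 = 240 per arm are evaluable.

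**Pooled against arm-specific standard error, one model, equal n.**

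- Pooled variance: (900 + 400 + 400)/3 = 566.7 (SD 23.8).
- Variance of an inclisiran-control difference as the pooled model reports it: 2 × 566.7/n = 1133.3/n.
- True variance: (900 + 400)/n = 1300/n.
- SE ratio: √(1133.3/1300) = 0.934, so 6.6% too small whatever n is.
- Coverage of a nominal 95% interval: 2Φ(1.96 × 0.934) − 1 ≈ 93.3%. One-sided error at nominal 2.5%: about 3.4%.

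| Evaluable per arm | SE, arm-specific | SE, pooled | Half-width, arm-specific | Half-width, pooled |
|---|---|---|---|---|
| 240 | 2.33 | 2.17 | 4.56 | 4.26 |
| 300 | 2.08 | 1.94 | 4.08 | 3.81 |

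**Simulation of the two-visit model.** A pooled unstructured covariance was fitted with 300 per arm, 6,000 runs and an assumed between-visit correlation of 0.6. The ratio of model SE to empirical SE was 0.943 with complete data and 0.938 with 20% of Day 270 values missing at random. Coverage was 93.8% and 93.5%. This agrees with the formula within simulation error.

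**Range.** With equal arms and SD ratio r, the SE ratio is √[2(r² + 2)/(3(r² + 1))].

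| Scenario | SE too small by |
|---|---|
| SD ratio 1.25 | 3.7% |
| SD ratio 1.5 (planning value) | 6.6% |
| SD ratio 2.0 | 10.6% |
| SDs 30/20, observed 220 control, 250 per inclisiran arm | 8.9% |
| SDs 30/20, observed 250 control, 220 per inclisiran arm | 4.3% |

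**Separate two-arm models.** With equal n the pooled variance is (900 + 400)/2 = 650, and 2 × 650 = 1300, so the ratio is 1.00 and the narrowing disappears.

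**The case against.** The SAP never says that the matrix is shared across arms; it is silent. Nor does it say that all three arms enter one model, and SAP 2.5.2 frames the hypotheses as one comparison with control per inclisiran arm. The SDs are planning values, and the real ratio could be smaller. SAP 2.5.3 keeps off-treatment LDL-C in the analysis, which mixes responders and discontinuers in the inclisiran arms. As an illustration, assume 10% of an inclisiran arm show no reduction, the rest are near −50%, and the SD within each subgroup is 20. The variance is then 400 + 0.1 × 0.9 × 50² = 625 (SD 25), and the narrowing is 1 − √(1433.3/1525) ≈ 3%. Heterogeneity is also already handled in the primary ANCOVA and in the other sensitivity analysis.

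Most of this stands as a limit on the size. It does not remove the gap. The SAP states arm-specific variance wherever it wants it, so silence here is ordinarily read as pooling, and the fixed effects in 2.5.5 read as a single model. If grouping or two-arm models were intended, the text still needs to say so.

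A reader might go further in two ways that the documents do not support:

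- **Group 3 against Group 2.** Pooling would make an LDL-C interval for this contrast too wide: √(1133.3/800) = 1.19. But no such contrast is planned. The Protocol summary (Other assessments) compares these groups on outcomes other than LDL cholesterol, and SAP 2.6.2 plans the comparison for CSQ-8 and PAM only.
- **Inflated error for the trial's claim.** The 3.4% is a property of the MMRM interval. SAP 2.5.2 rests the primary objective on the unequal-variance ANCOVA with Holm adjustment, and no success criterion is attached to the MMRM.

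**Conclusion.** The inconsistency is real and minor. Read in the ordinary way, SAP 2.5.5 gives the MMRM a variance assumption that SAP 2.5.2 calls improbable. The 6.6% narrowing and 93.3% coverage rest on three conditions: one model with all three arms, similar numbers observed per arm, and SDs of 30% and 20%.

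The practical weight is small. At 240 evaluable per arm the 95% half-width differs by 0.30 percentage points, against LDL-C reductions of about 50% in the phase III studies summarised in Protocol 1.1.4. The superiority conclusion would not change; what suffers is the comparison between the MMRM and the primary analysis. The concern carries over to SAP 2.5.6 in direction, but not necessarily in size, because that section refers to LDL-C change and adds multiple imputation.

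**What to change.** In SAP 2.5.5, state that the unstructured covariance is estimated separately by treatment group (in SAS, for example, TYPE=UN with GROUP=treatment on the REPEATED statement), and that the compound-symmetry fallback is also by treatment group. State that all three arms are fitted in one model. Carry the same specification into 2.5.6. Naming the degrees-of-freedom method at the same time would be tidy, but is optional.

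The cost is one model option. Two visits need three covariance parameters per arm, so nine in place of three: six more, with 900 participants planned. No data collection or other analysis changes.

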#### 2.5.6 Supplementary analyses

Supplementary analysis of LDL-C change from baseline to Day 270 will be performed using linear mixed-effect model for repeated measures (MMRM) analysis with multiple imputation as specified in section 2.5.5. This supplementary analysis will be performed by assessing supplementary estimand as mentioned below.

Intercurrent events (Study treatment discontinuation and Deviation in background treatment) will be handled similarly as mentioned in primary endpoint (Refer section 2.5.3) and additionally below mentioned strategy will be used for "Use of prohibited medications".

| ICE                                 | Strategy and justification of handling ICEs   | Missing value imputation  |
|-------------------------------------|---|---|
| Use of
prohibited
medications | Interest is in effect of treatment
regardless of changes in
concomitant lipid lowering
medication during study treatment.
Use of prohibited medications
(includes treatments which are | LDL-C data after this event will be
set to missing. Missing data after
this event will be imputed in same
way as mentioned in Appendix
5.5.1. |

| Novartis | 5 |
|----------|---|
| SAP      |   |

| ICE | Strategy and justification of handling ICEs  | Missing value imputation |
|-----|--|--------------------------|
|     | 
 
added to existing background
therapy during the study) will not
be allowed in the study and will
lead to study treatment
discontinuation.
 
The LDL-C data collected after the
use of any prohibited medication
will not be included in the
analysis.
 
 |                          |
|     | Hypothetical strategy with the
hypothetical scenario 'as if
patients would have not received
any prohibited medication.   |                          |

## 2.6 Analysis supporting secondary objectives

The secondary objectives of this study are to evaluate the implementation of inclisiran +/behavioural support compared to standard of care + behavioural support in a primary care setting using the following assessments that will be reported based on this SAP are:

- Measures of patient satisfaction using the validated CSQ-8 (Client Satisfaction Questionnaire) administered after treatment at day 90.
- Measures of patient activation and empowerment using the validated Patient Activation Measure (PAM) questionnaire administered after treatment at day 90.
- Measures of adherence to cardiovascular disease self-management using the validated Patient Activation Measure (PAM) questionnaire administered after treatment at day 90 and using assessment of medication adherence during the study period.
- Serious adverse event profile and adverse events leading to treatment discontinuation.

The following secondary endpoint will be analysed by Manchester University and are not covered by this SAP:

- A process evaluation conducted using the Consolidated Framework for Implementation Research (CFIR) which will explore inclisiran delivery at three levels:
  - > Feasibility and acceptability of delivery models for inclisiran to patients
  - Feasibility and acceptability of delivery models for inclisiran to providers (inner setting)
  - Wider 'transactability' of the proposed delivery models (outer setting)
  - The service costs of each delivery model
  - The acceptability and perceived sustainability of patient identification and referral routes

#### 2.6.1 Secondary endpoint(s)

The following are key secondary efficacy endpoints:

| Novartis | Confidential | Page 20 of 37           |
|----------|--------------|-------------------------|
| SAP      |              | Study No. CKJX839A1GB01 |

- Mean difference in total score using the validated CSQ-8 (Client Satisfaction Questionnaire) administered after treatment at day 90.
- Mean difference in total score using the validated Patient Activation Measure (PAM) questionnaire administered after treatment at day 90.
- Measures of adherence to cardiovascular disease self-management using the validated Patient Activation Measure (PAM) questionnaire administered after treatment at day 90 and using assessment of medication adherence during the study period.

All the analyses on above endpoints will be based on observed data only.

#### 2.6.1.1 The CSQ-8 PROMs Questionnaire

The Client Satisfaction Questionnaire© (CSQ) is a portfolio of measurement instruments (CSQScales®) designed to assess consumer satisfaction with health and human services, including governmental and public benefit programs and services.

Each scale measures the recipients' direct satisfaction with specific services offered and received within a particular time frame from a specific provider or service setting.

The CSQ-8 has 8 items and no subscales. and It reports a single score measuring a single dimension of overall satisfaction.

A total score is produced by summing all item responses, with a higher scores indicating higher satisfaction. The outcome is the mean difference in total score between treatment groups. For the CSQ-8 version, scores range from 8 to 32, with higher values indicating higher satisfaction. Scoring for other versions is similar after extrapolating for number of items.

The following endpoint will be analyzed with CSQ-8 PROMs Questionnaire data.

**Endpoint:** Mean difference in total score using the validated CSQ-8 (Client Satisfaction Questionnaire) administered after treatment at day 90. **Summary measure:** Mean difference in total scores between treatment groups.

#### 2.6.1.2 The PAM PROMs Questionnaire

This study will use the 13-point PAM questionnaire, which will be complimented by data on medication adherence to Inclisiran or standard of care recorded during the trial. The 13 item PAM consists of 13 statements relating to patients beliefs about health care, confidence in their management of health related tasks, and self-assessed knowledge of their condition.

For each statement patients are required to say how much they either agree or disagree on a response scale of 1–4, where 1 represents "strongly disagree" and 4 represents "strongly agree". Patients may also answer "non-applicable" which is scored as 0. A total score is created by summing the scores for the 13 statements and multiplying by 13/(13-n) where n is the number of statements answered as "non-applicable" or missing. The total is rounded to the nearest integer. The total score in the range [13,52] is then converted to a score in the range [0,100] using a calibration table. Note that if n>3, the calibrated score defaults to 51.

The continuous PAM scores are then categorized into four levels for descriptive purposes: according to the materials supplied by Insignia, scores less than 47.1 are level 1, scores between

47.1 and 53.2 are level 2, scores between 53.3 and 70.2 are level 3, and scores above 70.2 are level 4.

The following endpoints will be analyzed with PAM PROMs Questionnaire data.

- Endpoint: Mean difference in total score using the validated Patient Activation Measure (PAM) questionnaire administered after treatment at day 90. Summary measure: Difference between treatment groups in mean change in total scores from baseline to Day 90.
- Endpoint: Measures of adherence to cardiovascular disease self-management using the validated Patient Activation Measure (PAM) questionnaire administered after treatment at day 90 and using assessment of medication adherence during the study period. Summary measure: The frequency and percentages of subjects in the four levels of the PAM scores (below) will be summarized. Note that highly activated patients (level 3 and level 4) are more likely to adhere to cardiovascular self-management and thus medication adherence.

Level 1: Disengaged and overwhelmed

Level 2: Become aware but still struggling

Level 3: Taking action

Level 4: Maintaining behaviors and pushinng further

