This study will use the 13-point PAM questionnaire, which will be complemented by data on medication adherence to inclisiran or standard of care recorded during the trial. The 13 item PAM consists of 13 statements relating to patients beliefs about health care, confidence in their management of health related tasks, and self-assessed knowledge of their condition (Hibbard and Gilburt, 2014). For each statement patients are required to say how much they either agree or disagree on a response scale of 1–5, where 1 represents "strongly disagree", 4 represents "strongly agree" and 5 indicates that the statement is "not applicable" to them.

A standardised spreadsheet in excel is used to score the PAM. Responses are used to generate a continuous score from 0 to 100 where higher scores indicate that the patient is more activated (Hibbard and Gilburt, 2014). Where participants have answered that a statement is not

Novartis	Confidential	Page 79 of 85
CLINICAL TRIAL PROTOCOL: Version 02	Protocol No. CKJX839A10	B01 (VICTORION Spirit)

applicable to them the data is treated as missing. A total score is generated where participants have answered at least 10 out of the 13 questions.

The continuous PAM scores are then categorised into four levels for descriptive purposes using a calibration table. Those who fall into Level 1 are defined as passive recipients of care who do not understand that they can play an active role in their own healthcare. Level 2 includes patients who lack the basic knowledge and confidence to effectively self-manage (for example they may not understand the treatment options available to them or what their medications do). Level 3 includes those who have a basic knowledge about their health but they lack the confidence and skills to engage in positive self-manage but who may need support during times of personal stress or health crisis (Hibbard et al, 2005).

The PAM has been found to be a valid and reliable measure in people with long-term conditions, such as those attending cardiac rehabilitation, (Hibbard et al, 2004) and in those patients with multi-morbidity (Skolasky et al, 2011).

Below are some statements that people sometimes make when they talk about their health. Please indicate how much you agree or disagree with each statement as it applies to you personally by circling your answer. Your answers should be what is true for you and not just what you think others want you to say.

If the statement does not apply to you, circle N/A.

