#### 2.6.2 Statistical hypothesis, model, and method of analysis

The key secondary variables will be analyzed as follows:

- Mean difference in total score using the validated CSQ-8 (Client Satisfaction Questionnaire) administered after treatment at day 90 between the groups will be analyzed using ANOVA. The test statistics, mean difference, 95% confidence interval and the p-value obtained using the ANOVA will be presented.
- The comparison between inclisiran and inclisiran + behavioural support also will be done and presented as mentioned above. Inclisiran arm will be considered as control for this analysis.
- The descriptive statistics for the total CSQ score will be provided for each treatment group.
- Mean difference in total score using the validated Patient Activation Measure (PAM) questionnaire administered after treatment from baseline today 90 will be analyzed using ANCOVA model. ANCOVA model which assumes unequal variances for treatment group will be used. The model will include the fixed effects of treatment group with baseline total scores as a covariate. The estimate and corresponding 2-sided 95% confidence intervals of mean difference between treatment groups will be calculated. p-value for hypothesis test for mean difference will also be provided. The FAS will be used for this analysis.
- The comparison between inclisiran and inclisiran + behavioural support also will be done and presented as mentioned above. Inclisiran arm will be considered as control for this analysis.

| Novartis | Confidential | Page 22 of 37           |
|----------|--------------|-------------------------|
| SAP      |              | Study No. CKJX839A1GB01 |

• Measures of adherence to cardiovascular disease self-management using the validated Patient Activation Measure (PAM) questionnaire administered after treatment at day 90 and using assessment of medication adherence during the study period will be summarized by providing the frequency and percentages of subjects in the four levels of the PAM scores (below) by visit and treatment. Note, highly activated patients (level 3 and level 4) are more likely to adhere to cardiovascular self-management and thus medication adherence.

Level 1: Disengaged and overwhelmed

Level 2: Become aware but still struggling

Level 3: Taking action

Level 4: Maintaining behaviors and pushinng further

• Also frequency and percentage of subjects completed each item of PAM questionnaire will be summarized by visit and treatement.

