#### 2.6.3 Handling of missing values

No imputation will be applied if the scores are missing at a visit in any the questionnaire. The proportion of missing data will be included in summaries to aid interpretation.

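### The SAP scores PAM forms with more than 3 of 13 items unanswered or not applicable as a constant 51, where the protocol generates no score

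*SAP*

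**What the plan says.** SAP 2.6.1.2 sums the 13 PAM items (scored 1 to 4, not applicable scored 0), multiplies by 13/(13 − n), and converts the result to a 0–100 score through a calibration table. Here n counts items that are not applicable or missing. It then adds: "Note that if n>3, the calibrated score defaults to 51". Its cut-offs place scores below 47.1 in Level 1, 47.1 to 53.2 in Level 2, 53.3 to 70.2 in Level 3 and above 70.2 in Level 4.

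Protocol 16.3 (Appendix 3) says that where a statement is marked not "applicable to them the data is treated as missing", and that "A total score is generated where participants have answered at least 10 out of the 13 questions". It also says: "A standardised spreadsheet in excel is used to score the PAM". That spreadsheet is not among the documents, and neither document says where 51 comes from.

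On the key secondary endpoints, PAM included, SAP 2.6.1 says: "All the analyses on above endpoints will be based on observed data only". SAP 2.6.3 rules out imputation of missing questionnaire scores and says: "The proportion of missing data will be included in summaries to aid interpretation".

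The score is used twice. SAP 2.6.2 compares the change from baseline to Day 90 by ANCOVA: "The model will include the fixed effects of treatment group with baseline total scores as a covariate". For the adherence endpoint, SAP 2.6.1.2 names this summary: "The frequency and percentages of subjects in the four levels of the PAM scores (below) will be summarized".

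**The concern.** The two documents treat the same forms in opposite ways, and the SAP's rule replaces the patient's answers with a constant that nobody observed. PAM is a key secondary endpoint and, with CSQ-8, one of the two outcomes that drive the sample size (protocol 12.8, SAP section 3).

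Three things follow if the rule stands. Equal shares of defaulted forms in the arms pull a true difference towards zero. Unequal shares move the comparison even when there is no true difference. And every defaulted form is counted in Level 2, outside Levels 3 and 4, which the SAP reads as more likely to be adherent.

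The existing safeguards are partial. Participants are contacted about missing responses (protocol 4.5), but that does not remove genuine not-applicable answers, which the form invites. SAP 2.6.2 tabulates completion item by item, which does not count forms with n above 3. The missing-data summary in SAP 2.6.3 would not show a form scored 51 as a missing score.

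**Working it through.** **1. Do the rules concern the same forms?** n > 3 means 13 − answered > 3, that is, 9 or fewer answered. This holds for every count from 0 to 13, so the sets are identical: no score under the protocol, 51 under the SAP. And 47.1 ≤ 51 ≤ 53.2, so 51 is Level 2.

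**2. Does 51 reflect the answers?** With nine items answered, proration would give 36 × 13/9 = 52 (the maximum raw score) if all are 4, and 9 × 13/9 = 13 (the minimum) if all are 1. Both become 51.

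**3. Effect on one patient, from the SAP cut-offs alone.** If the Day 90 form is defaulted, a patient above 70.2 at baseline shows a fall of more than 70.2 − 51 = 19.2 points. A patient below 47.1 shows a rise of more than 51 − 47.1 = 3.9.

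**4. The plan's sample size.** Effect size 0.3, 90% power, one-sided 0.025: 2 × (1.960 + 1.282)²/0.3² gives 234 per arm, and 234/0.8 gives 293. With 240 evaluable (300 less 20%) the power is 90.8%. The planned 300 reproduces and is not in dispute.

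**5. Effect on the comparison.** The documents give no PAM mean, SD, baseline correlation or share with n > 3. Assumed: SD 15, correlation 0.5, 240 per arm, scores limited to 0–100, baseline forms defaulted independently at the average share. The ANCOVA with arm-specific variances was simulated (3,000 replicates for equal shares and for step 6, 4,000 for unequal shares).

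Equal shares, true difference 4.5 points (0.3 × 15):

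| Mean | Share | Estimate with 51 | Power with 51 | Power if missing |
|---|---|---|---|---|
| 51 | 2% | 4.40 | 96.1% | 95.8% |
| 51 | 5% | 4.24 | 95.4% | 94.9% |
| 51 | 10% | 4.06 | 94.1% | 92.8% |
| 62 | 2% | 4.38 | 95.4% | 96.0% |
| 62 | 5% | 4.26 | 94.4% | 95.1% |
| 62 | 10% | 4.01 | 90.3% | 91.8% |

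The estimate shrinks by roughly the factor (1 − f). Power differs by at most 1.5 points, in either direction. A cruder calculation without baseline adjustment, over means 51 to 65 and SDs 12 to 15, gives at 10% a power of 82.0% to 87.5% with the default, against 87.7% with scores missing.

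Unequal shares, no true difference. Approximate shift = (f1 − f0) × (51 − mean), with f1 the test and f0 the control share:

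| Mean | Control / test share | Formula | Simulated shift | Two-sided error |
|---|---|---|---|---|
| 51 | 5% / 15% | 0 | 0.00 | 5.0% |
| 56 | 5% / 15% | −0.50 | −0.47 | 6.8% |
| 60 | 2% / 5% | −0.27 | −0.23 | 5.5% |
| 60 | 5% / 15% | −0.90 | −0.92 | 12.4% (11.1% in a second run) |
| 62 | 5% / 15% | −1.10 | −1.09 | 14.2% |

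Reversing the shares at mean 60 gives +0.92. With scores set to missing, the error is 5.1% to 5.2% in all of these.

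**6. When incompleteness depends on the score.** Mean 60, no true difference, incompleteness at Day 90 rising by a factor e for each SD below the mean, shares 5% / 15%: the default is biased by +0.42 (6.6% error) and exclusion by +1.23 (17.6%). At 2% / 5% the figures are +0.21 (5.4%) and +0.40 (6.6%). At 5% / 5% both are about nil.

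**7. Level table.** For a normal score with mean 60 and SD 15, 13.1% lie in Level 2 and 67.4% in Levels 3–4. With share f defaulted, Level 2 = f + (1 − f) × 13.1%, and Levels 3–4 = (1 − f) × 67.4%:

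| Share | Level 2 | Levels 3–4 |
|---|---|---|
| 2% | 14.9% | 66.0% |
| 5% | 17.5% | 64.0% |
| 15% | 26.2% | 57.3% |

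**The case against.** The strongest reply is that 51 may be the licensed instrument's own scoring rule. The protocol refers to a scoring spreadsheet and the SAP to the supplier's materials, and neither file is available here. Appendix 3 never states what happens to forms with fewer than 10 answers, protocol 12.5.1 leaves full details to the SAP, and SAP section 4 on changes has no readable entry, so a recorded change cannot be excluded. All of that is true. It leaves the documents in conflict: if the spreadsheet returns 51, Appendix 3's two sentences also need reconciling.

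It can also be said that proration fills in unanswered items too, so the observed-data sentence cannot be decisive. But proration uses the answers given, and the constant does not. SAP 2.6.3 suggests that unreturned forms stay missing. This narrows the forms affected, although a wholly blank form (n = 13) has no defined proration and is not addressed.

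The harm is assumed. No mechanism for unequal shares has been shown, and the larger error rates need 5% against 15%. The Holm procedure covers only the LDL-C comparisons, no error control is stated for PAM, and the levels are descriptive. This stands, and it limits the weight of the point.

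Setting scores to missing is also not always less biased: step 6 shows it doing worse when low scorers leave more items blank and shares differ. This stands too, and the SAP should state the assumption.

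**Conclusion.** The point holds. The SAP assigns a score to exactly the forms that the protocol leaves unscored, and the constant is at odds with the SAP's own statements on observed data and no imputation. Confidence is high on the conflict and on following the protocol's rule, but not on the size of the bias.

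The effect could be negligible: nil if the PAM mean is near 51, and 0.2 to 0.3 points at mean 60 with shares of 2% and 5%. It reaches about 0.9 points, with 11–12% two-sided error, only under a large imbalance (5% against 15%). These figures rest on the assumed SD of 15, correlation of 0.5 and means of 51 to 62. The level table is distorted whatever the balance, because every defaulted form becomes Level 2. The change should be made before database lock, as a correction to a key secondary endpoint. The primary endpoint and the planned sample size do not depend on it.

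**What to change.** Delete the default-to-51 sentence from SAP 2.6.1.2. Set the PAM score and level to missing when n exceeds 3, at baseline and at Day 90, as Appendix 3 implies. Identify these forms by item count and not by the value 51, since a complete form may calibrate to 51 and the spreadsheet may itself return it. State where 51 came from and reconcile Appendix 3 if the spreadsheet is the source. Report the number of forms with n above 3 by arm and visit, split into not applicable and skipped. State that exclusion assumes ignorable incompleteness, and keep the 51 rule at most as a sensitivity analysis.

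The text cost is one SAP sentence, one line of derivation code, a small count table and the statement of the assumption. The cost in patients can be larger, because the ANCOVA needs both visits. Of 240 per arm, the loss runs from 240f (same patients at both visits) to 240[1 − (1 − f)²] (visits independent):

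| Share per visit | Patients lost per arm |
|---|---|
| 2% | 5–10 |
| 5% | 12–23 |
| 10% | 24–46 |
| 15% | 36–67 |

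At the upper end this is not a small loss. The change is made to report what was measured; it does not buy power.
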